6.2.3. Safety Population

All participants who are treated with any amount of SDF will be included in the Safety Population. Participants will be summarized according to the treatment they received. Safety analyses will be conducted using the Safety Population.

6.2.4. Intent-to-Treat Population #2 (ITT2) - Interim Participants

The ITT2 Population will include all participants randomized to receive study drug and included in the interim analysis. Participants will be summarized according to their randomized treatment and not the treatment they receive. The ITT2 Population will be used for efficacy analyses.

6.2.5. Per Protocol Population #2 (PP2) - Interim Participants

The PP2 Population will be limited to subjects included in the interim analysis who complete the baseline, 3-month, and 6-month dental examinations within the originally-specified windows. The PP2 Population will be used for supportive analyses of efficacy.

6.3. Global Conventions and Definitions

6.3.1. Computing

All data listings, summaries, figures, and statistical analyses will be generated using SAS version 9.4 or higher (SAS Institute, Cary, NC).

6.3.2. General Statistical Methods

For continuous variables, the number of non-missing observations, mean, standard deviation (SD), median, and minimum and maximum values will be presented. The minimum and maximum values will be presented with the same precision as the data. The mean and median will be presented with a precision of one decimal place more than the data. The standard deviation will be presented with a precision of two decimal places more than the data.

For categorical variables, the number/frequency and percentage within each category of the parameter will be presented. For each parameter, all categories will be shown, and for categories with a number/frequency of zero (0), only the number, without percentage, will be presented. Percentages will be presented with one decimal place.

6.3.3. Listing Conventions

In general, listings will be sorted in the following order:

- Treatment
- Participant
- Parameter
- Study Day

All data collected on the eCRFs will be presented in the data listings.

6.3.4. Table Conventions

In general, summaries of the data will be presented by treatment group with the treatment group labels displayed as follows in the table outputs:

SDF (N=XX)	Control (N=XX)
---------------	-------------------

There is one exception, whereby baseline tables will additionally include an “Overall” column, i.e., SDF and Control combined:

SDF (N=XX)	Control (N=XX)	Overall (N=XX)
---------------	-------------------	-------------------

6.3.5. Baseline and Study Day

Baseline values will be defined as the last available non-missing result prior to SDF administration. Assessments carried out on the day of first study drug administration (SDF application) are considered to have taken place before the SDF application if the corresponding times have not been recorded.

Study day will be calculated as the number of days from first SDF administration.

For events/assessments on or after study drug (SDF) administration:

- Study day = date of event (or date of assessment) – date of first SDF administration + 1.

For events/assessments before study drug (SDF) administration:

- Study day = date of event (or date of assessment) – date of first SDF administration.

6.3.6. Conventions for Missing or Partial Dates

In the rare case that an AE start date or time is missing, and it is unclear whether the AE is treatment emergent or not, then a conservative approach will be taken, and it will be assumed that the AE occurred after study drug administration.

If a prior or concomitant medication end date or time is missing and it is unclear whether the medication is prior or concomitant, then a conservative approach will be taken, and it will be assumed that the medication was taken on or after study drug administration.

If a medical condition end date or time is missing and it is unclear whether the medical condition is previous or ongoing, then a conservative approach will be taken, and it will be assumed that the medical condition was still active on or after study drug administration.

Where the Date of Birth is missing, the following convention will be used:

- Where the day is missing and month and year are available, the day will be completed as the 15th. For example, Date of Birth specified as --JAN1980 will be completed as 15JAN1980.
- If the day and month are missing and the year is available, the day and month will be completed as 02JUL (the 183rd day of the year). For example, Date of Birth specified as ----1980 will be completed as 02JUL1980.

All dates presented in the individual participant listings will be as recorded on the Electronic Case Report Form (eCRF).

6.4. Visit Windows

6.4.1. Visit and Intermediate Contact Windows

Visit and intermediate contact windows as initially defined in the protocol are: +/- 19 days for the 3-month in-person visit (71-110 days post-baseline), 6-month in-person visit (161-201 days post-baseline), and 8-month in-person visit (221-262 days post-baseline); +/- 10 days for the 1.5-month telephone-based intermediate contact (35-55 days post-baseline), 4.5-month telephone-based intermediate contact (125-146 days post-baseline), and 7-month telephone-based intermediate contact (200-222 days post-baseline).

6.4.2. 3-Month, 6-Month, and 8-Month Contacts During COVID-19 Pandemic

Due to the COVID-19 pandemic and associated illnesses, precautions, and shutdowns, some study subjects were unable to be seen for in-person visits within the study windows. To maintain contact with the subjects and ensure data were collected when possible, phone contacts occurred within the windows of the 3-month, 6-month, and 8-month visits. Although the dental examinations could not take place during these contacts, the questionnaire-based responses could be collected (DDQ, P-CPQ, FIS, Treatment Satisfaction and Acceptability). A subject may have two sets of data for the same ‘visit’ if an in-person visit subsequently occurred after the data were collected via phone. If an in-person visit occurred within the standard visit window (see [Section 6.4.1](#)), the data collected at the in-person visit will be used, otherwise the data collected via phone will be used.

6.5. Participant Disposition

Participant disposition will be summarized by treatment group and overall, where appropriate, for the Screened Population. The following information will be reported:

- Number of participants for the following category:
 - Screened
- Number and percentage of participants for the following categories:
 - Randomized
 - Treated
 - Not Treated
 - Completed the study
 - Discontinued the Study
 - Reasons for study discontinuation
- Number and percentage of participants included in, and excluded from, each study population together with the reasons for exclusion from the analysis set.
- Number and percentage of participants who completed / discontinued treatment, including the reasons for treatment discontinuation.
- Number and percentage of participants who met / did not meet all eligibility criteria, together with the criteria not met.

- Number and percentage of participants who failed screening prior to randomization, including the primary reason for screen failure.
- Number and percentage of participants at each site.

All disposition data will also be listed.

6.6. Protocol Deviations

A listing of protocol deviations will be provided within Appendix 16.2 of the CSR.

6.7. Demographic and Baseline Characteristics

The comparability of treatment groups with respect to participant demographics and baseline characteristics will be assessed in a descriptive manner, but no formal statistical testing will be performed. Standard continuous or categorical variable summaries will be presented by treatment group for demographic and baseline characteristics in each of the analysis populations.

Standard descriptive statistics will be presented for the demographic continuous variables, e.g.:

- Number of Children Living with You
- Number of Adults Living with You

Total counts and percentages of participants will be presented for the demographic categorical variables including:

- Age (1, 2, 3, 4, 5 years)
- Sex
- Race
- Ethnicity
- Primarily non-English spoken at home
- Study site
- Is a Household Adult Employed
- Number of Children Living with You
- Number of Adults Living with You
- Household Income

Standard descriptive statistics will be presented for the baseline characteristic continuous variables:

- Number of study teeth per subject
- Number of study lesions per subject
- dmfs (number of decayed, missing, and filled surfaces)
- dmft (number of decayed, missing, and filled teeth)
- P-CPQ FL
- P-CPQ EW
- P-CPQ SW
- FIS
- FIS PE

- FIS PF
- FIS FC
- Child's Teeth and Mouth Health
- How much is Child's Overall well-being affected by the condition of his/her teeth, lips, jaw or mouth
- How Much is Family's Daily Life Affected your child's teeth lips, jaws or mouth

Total counts and percentages of participants will be presented for the baseline characteristic categorical variables of:

- Entry criteria met
 - Age <3 S-ECC: Any Caries
 - Age 3-5 S-ECC: upper anterior dmfs \geq 1
 - Age 3 S-ECC: dmfs \geq 4
 - Age 4 S-ECC: dmfs \geq 5
 - Age 5 S-ECC: dmfs $>$ 5
- Number of study teeth per subject
- Number of study lesions per subject
- Lesion location
 - Tooth
 - Anterior / Posterior
 - Maxillary / Mandibular
 - Surface
- ICDAS severity score for enrolled lesions
- Maximum ICDAS severity score for subject
- Frequency Child's Teeth are Brushed
- Who Brushes Child's Teeth
- Child Uses Fluoride Toothpaste
- Child Uses Prescription High-Fluoride Toothpaste
- Fluoride Painted/Put on Child's Teeth
- How Often Does Child Get Sugary Drinks
- How Often Does Child Get Sugary Snacks
- How Often Does Child Drink Water
- Parent's Satisfaction in Appearance of Child's Teeth
- Child's Satisfaction in Appearance of Child's Teeth
- Have Any of Your Children Had Cavities Fixed at Hospital
- Have Any of Family or Friend's Children Had Cavities Fixed at Hospital
- Do You Have Any of Your Own Teeth
- Have You Had Cavities, Fillings, or Teeth Pulled in Last Two Years

All demographic and baseline characteristic data will also be listed.

6.8. Medical History

All medical history data will be listed.

6.9. Prior and Concomitant Medications

All prior and concomitant medications will be listed.

6.10. Exposure

The number of SDF applications administered will be summarized categorically (0, 1, 2) by treatment group for the Safety and ITT and ITT2 Populations. The number of applications administered will be listed for each participant. Missing data will not be imputed.

6.11. Efficacy Analyses

All efficacy endpoints will be analyzed using the ITT and ITT2 populations. Additional analyses will be performed on the PP and PP2 populations.

The null hypothesis is no difference between the treatment groups and the alternative hypothesis is there is a difference between treatment groups. All statistical comparisons will be made using a two-sided test. The interim and final analyses will be conducted using p-value thresholds of 0.000001709 and 0.00099938, respectively. The overall type I error for interim and final primary endpoint analysis is two-sided $\alpha=0.1\%$.

Several categorical variables that are to be used as covariates in the GEE model will have categories collapsed due to small sample sizes. Race and ethnicity will be combined to form a single combined variable defined as: Hispanic or Latino if a subject indicated as such for ethnicity, multiracial if more than one race was selected, Black, White, “Asian or ‘American Indian or Alaska Native’ or ‘Native Hawaiian / Other Pacific Islander’”, “Not Reported” or Unknown”. Within the ‘tooth’ variable, lower incisors (LL1, LL2, LR1, LR2) will be combined into a single category and LR6 will be combined with LR5 for the imputation models for the lesion arrest outcomes, and combined into upper jaw / lower jaw and anterior teeth (upper and lower central incisors, lateral incisors, and canines) / posterior teeth (upper and lower molars on the) variables for the imputation models for the presence of tooth pain outcomes. For the imputation models for the presence of tooth pain outcomes, child ages 1 and 2 years will be combined.

The primary method for handling missing data for 6-month and 8-month efficacy analysis will be to use a multiple imputation analysis. Missing data follow a non-monotone missing pattern. The imputation will use fully conditional specification (FCS) methods. Imputations for lesion arrest and lesion pain will be based on race/ethnicity, gender, age, trial site, initial ICDAS score, tooth location, and lesion arrest results from prior visits using a logistic regression model. Imputations for the subject-level pain score and family outcomes will be based on race/ethnicity, gender, age, trial site, maximum initial ICDAS score for the subject, a non-arrested/arrested indicator for the subject (non-arrested if any of the subject’s study lesions are not arrested) at the ‘current’ visit or at the most recent prior visit if the ‘current’ visit is missing, and results at prior visits for the

outcome using a predictive mean matching model. Missing at random (MAR) will be assumed. Twenty-five imputed datasets will be created, and results from the analyses performed on each imputed dataset will be combined using standard methods via Proc MIAnalyze.

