12.4.2 Missing data

As noted in [Section 5.5](#), any lesions removed from the trial due to the “early exit strategy” will be considered to be treatment failures – non-arrest of the lesion and presence of pain and/or infection requiring removal of the tooth from the study – and not considered to be missing data.

The primary method for handling missing data will be to use a multiple imputation analysis, with imputations based on race/ethnicity, gender, age, trial site, initial ICDAS score, tooth location, treatment, and most recent prior visit results will be performed. Twenty-five imputed datasets will be created, and results will be combined using standard methods.

A sensitivity / tipping point analysis will also be performed to evaluate the MAR (missing at random) assumption for the missing primary efficacy outcome (caries arrest at approximately 6 months). A pattern-mixture approach to the missing data imputation (missing not at random, MNAR) will be applied to the logistic regression model used for imputing the missing caries arrest at approximately 6 months outcome from the variables described above. To represent MNAR, a range of shift parameters will be used to adjust the log odds ratios for the SDF-treated group. The tipping point will be identified as the amount of shift needed to change the statistical significance of the treatment comparison using the primary efficacy analysis. The size of the shift required to change the statistical significance will be used to gauge the plausibility of the MAR assumption.

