6.11.4. Secondary Efficacy Hypotheses, Endpoints, and Analyses

The gatekeeping procedure will assess the hypotheses associated with the two key secondary endpoints in the following prescribed hierarchy. Each endpoint will be assessed using a two-sided $\alpha=0.1\%$ significance level, however the second endpoint in the hierarchy below will be gated by the first endpoint meeting significance. Otherwise, no inference will be drawn on the second endpoint in the hierarchy below, however results with p-values will still be calculated and presented in the table outputs.

1. Secondary Endpoint #1: Cavitated Caries Lesion Arrest at 8 months (Aim 2)

This secondary endpoint will be tested first. The same GEE model for binary outcomes as used for Aim 1 will be used to compare the proportion of arrested lesions at 8-months to examine Aim 2.

2. Secondary Endpoint #2: Pain (Aim 3)

This secondary endpoint will be tested second only if the first secondary endpoint reaches statistical significance.

Aim 3: At the 8-month visits, the proportion of treated lesions that have experienced pain during the follow-up period before or at the visit will be compared between the SDF and placebo-treated groups using GEE models with a logit link for the lesion-specific binary outcomes yes/no lesion pain at each visit, using an exchangeable correlation to account for non- independence among multiple treated lesions within a participant. The GEE models will include study site as a covariate due to stratified randomization by site.

Other Sub-Aim Secondary Endpoint Analyses:

For Sub-Aim 2a (Cavitated caries lesion arrest at 3 months), the same GEE model for binary outcomes as used for Aim 1 will be used to compare the proportion of arrested lesions at 3 months to examine Aim 2a. Sub-Aim 2a is not included in the hierarchical testing strategy.

For Sub-Aim 2b (Stability of the effect of one application of 38% SDF on caries lesion arrest between 3 and 6 months), a longitudinal (repeated measures) model for binary data that incorporates both the correlation within each subject at each time and across the time points will be used to compare the proportion of arrested caries lesions at 3 and 6 months. Study site will be included as a covariate due to stratified randomization by site.

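### The SAP limits multiple imputation to months 6 and 8, so the month-3 arrest comparison uses available lesions only, and the dataset for the month-3 versus month-6 model is not stated

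*SAP*

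**What the plan says.** Protocol 12.4.2 makes multiple imputation the general method, with no visit named: "The primary method for handling missing data will be to use a multiple imputation analysis, with imputations based on race/ethnicity". Its predictor list goes on to include treatment and the most recent prior visit's results.

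SAP 6.11 narrows this: "The primary method for handling missing data for 6-month and 8-month efficacy analysis will be to use a multiple imputation analysis". The same paragraph says "Missing data follow a non-monotone missing pattern" and "The imputation will use fully conditional specification (FCS) methods", assumes missing at random, and plans 25 imputed datasets. For lesion arrest, the predictors are race/ethnicity, gender, age and site, followed by "initial ICDAS score, tooth location, and lesion arrest results from prior visits using a logistic regression model". Treatment arm is not in that list.

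Month 3 is nevertheless analysed. SAP 6.11.4 applies the Aim 1 GEE to month-3 arrest (Sub-Aim 2a). It also plans "a longitudinal (repeated measures) model for binary data that incorporates both the correlation within each subject at each time and across the time points", "used to compare the proportion of arrested caries lesions at 3 and 6 months" (Sub-Aim 2b), again with site as the covariate. SAP 6.11.5 adds covariate models that include month 3. Stability of arrest from month 3 to month 6 is a secondary hypothesis in Protocol 12.1. Neither document gives a missing-data rule specific to month-3 arrest. SAP section 9, which records changes from the protocol, does not mention the restriction.

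**The concern.** SAP 6.11 puts every efficacy endpoint on the ITT population. If month 3 is not imputed, the month-3 GEE sees only lesions examined in window, plus those already counted as early-exit failures. Months 6 and 8 see every ITT lesion. The three arm comparisons would be read as one series but would describe different sets of lesions.

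The imputation model treats missing at random as conditional on initial ICDAS score, tooth location, age and other variables. The month-3 GEE conditions on arm and site only. An available-data GEE is not generally valid when missingness depends on predictors of arrest that it leaves out.

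Missing month-3 examinations are a real prospect. SAP 6.4.2 says that during the pandemic some month-3, -6 and -8 visits were replaced by telephone contacts, at which no dental examination was possible. Questionnaires survive such a contact; dentin hardness does not.

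For Sub-Aim 2b the gap is one of specification. Different input datasets can give different answers to a question about no change, and the SAP does not fix the choice in advance.

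**Working it through.** **The plan's own figure.** The only design figure is the 1144 participants, and this point does not depend on it. It reproduces: 55% versus 45%, two-sided alpha 0.1% and 80% power give 852 lesions per arm. The design effect is 1 + (3 − 1) × 0.5 = 2. Then 852 × 2 / 3 = 568 children per arm, or 1136 in total.

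**Inputs for this point.** The documents give no month-3 missing share and no arrest rate among unexamined lesions. Protocol 12.2 anticipates 10% attrition over the whole trial. All values of f and g below are therefore assumptions.

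**Formula.** Let f be the share of an arm's lesions missing at month 3, and g the arrest rate among examined lesions minus that among unexamined lesions.

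- All lesions: p_all = (1 − f) × p_obs + f × p_miss.
- Error of the observed-only proportion: p_obs − p_all = f × (p_obs − p_miss) = f × g.

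Error in percentage points, by f and g:

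| f | g = 0 | g = 5 | g = 10 | g = 20 |
|---|---|---|---|---|
| 5% | 0 | 0.25 | 0.5 | 1.0 |
| 10% | 0 | 0.5 | 1.0 | 2.0 |
| 20% | 0 | 1.0 | 2.0 | 4.0 |
| 30% | 0 | 1.5 | 3.0 | 6.0 |

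**Sub-Aim 2a (between arms, month 3).** The error in the risk difference is f × g in the SDF arm minus f × g in the placebo arm. With f = 10% in both arms and g = 20 and 10 points, it is 2 − 1 = 1 point. With equal f × g it cancels.

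**Sub-Aim 2b (month 3 to month 6).** If observed-only month 3 were set against a correctly imputed month 6, one arm's apparent change would be off by −f × g with no lesion changing.

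A simulation checks this. Assumptions: 1716 independent lesions, 200 replicates, and a binary covariate split 50/50. Arrest is 65% or 45% by covariate, with no true change on average. Missingness at each visit is 5% or 25% by covariate, 15% overall.

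- p_obs = (0.95 × 65 + 0.75 × 45) / 1.70 = 56.2%.
- p_miss = (0.05 × 65 + 0.25 × 45) / 0.30 = 48.3%.
- Expected artefact: −0.15 × 7.8 = −1.2 points.

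| Data used | Mean change, points |
|---|---|
| Observed month 3, imputed month 6 | −1.14 |
| Imputed at both visits | +0.04 |
| Observed at both visits | +0.04 |

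Only the mixed dataset produces the artefact. The observed-only result at both visits depends on the two visits having the same missingness pattern, as simulated.

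**Why deleting the visit restriction is not enough.** Trial lesions are all soft at baseline by inclusion, so no prior-visit arrest result varies before month 3. With arm also absent from the SAP's list, month-3 values would be imputed from baseline covariates alone. As an illustration, suppose the design rates of 55% and 45% applied at month 3, with 10% missing at random in each arm. Both arms' missing lesions would then be imputed at about 50%, and the difference would become 0.9 × 10 + 0.1 × 0 = 9 points instead of 10.

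**The case against.** A reader might infer that Sub-Aim 2b does set observed-only lesions at month 3 against all lesions at month 6, so that part of the reported change is an artefact. The documents do not support that. SAP 6.11.4 is silent on the model's input data. Observed data at both visits or completed data at both visits are equally open. The SAP text even leans towards completion: month-3 arrest is a prior-visit predictor for month 6, and fully conditional specification ordinarily fills an incomplete predictor. An artefact also requires month-3 missingness to be related to arrest, which nothing in the documents shows.

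Other points on that side stand:

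- Lesions that exit before month 3 can count as failures at month 3 as well as later, since SAP 6.11.1 tracks exit timing.
- Month-3 pain (Sub-Aim 3a) cannot simply be called complete-case. The outcome accumulates over follow-up, so a missed examination is not automatically a missing outcome.
- The list in SAP section 9 is not worded as exhaustive.
- The plan's 10-point yardstick is a between-arm difference, whereas f × g is a shift within one arm.
- Sub-Aims 2a and 2b lie outside the gated hierarchy, and Protocol 3.2.2 says the secondary outcomes are not meant to support labeling claims.

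A longitudinal model fitted by likelihood can be valid under missing at random without imputation. That helps only partly: the SAP does not name a likelihood method, and the model carries site as its only named covariate, while the SAP's missing-at-random assumption rests on several more.

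None of this supplies a rule for missing month-3 arrest, and the restriction to months 6 and 8 is explicit.

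**Conclusion.** The point holds as a narrow one. The SAP restricts multiple imputation to two of the three follow-up visits that it analyses, departs from Protocol 12.4.2 in doing so, and does not record the departure. Followed literally, Sub-Aim 2a is an available-lesion analysis adjusted for site only. It can be biased under the SAP's own assumption and is not on the same lesions as months 6 and 8. For Sub-Aim 2b the defect is an unstated dataset, not a demonstrated bias.

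The size cannot be computed from the documents. At an assumed 10% missing and a 10 to 20 point gap, the error in one arm's month-3 proportion is 1 to 2 points, and the same shift enters the month-3 to month-6 change only if the datasets are mixed. It is zero if missingness is unrelated to arrest, and equal errors cancel in a between-arm risk difference. Larger values need larger assumed missing shares or gaps, for which the documents give no figure. The primary analysis and the two gated secondary tests are not affected.

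**What to change.** 1. In SAP 6.11, extend the imputation sentence to the 3-, 6- and 8-month efficacy analyses.
2. State that the imputation model for month-3 arrest includes treatment arm, as Protocol 12.4.2 does, and arrest at the other visits, including later ones.
3. Run Sub-Aims 2a and 2b on the same 25 imputed datasets, with the same lesions at each visit and early exits counted as failures from their exit date. Do the same for month-3 pain in Sub-Aim 3a where that outcome is actually missing.
4. List the change in SAP section 9.

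The cost is SAP wording and slightly more analysis work. No new data are needed, and a fully conditional run that uses month-3 arrest as a predictor would ordinarily already produce imputed month-3 values.

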4. SAMPLE SIZE

The population will be children 12-71 months of age at the baseline caries examination attending early childhood education programs or recruited from clinics associated with the Michigan, Iowa or New York clinical trial sites.

The primary outcome of this trial is the proportion of arrested caries lesions approximately 6 months from the baseline visit (i.e., lesions that have changed from soft to hard over the trial period according to the ICDAS II activity criteria). A 10% difference in the proportion of arrested caries lesions between the SDF and placebo groups will be considered clinically significant. Prior studies in the literature of SDF using this outcome in primary cavitated lesions have shown a wide range for the proportion of arrested caries lesions for both SDF-treated and placebo-treated or untreated lesions; therefore the 10% difference in proportions was calculated assuming 55% versus 45% arrested caries lesions for SDF compared to placebo. In prior studies, an average of 4 lesions was treated per participant, with a within-participant correlation of 0.5; we are conservatively assuming 3 lesions per participant. The sample size calculations used a 2-sided test for a difference in proportions with cluster randomization (participant as the cluster) at significance level $\alpha=0.1\%$, with 80% power to detect a superiority difference of 10% for SDF compared to placebo. The calculations also account for the use of an early stopping rule for efficacy and futility. The interim analysis will be performed after approximately half of the sample has completed the 6-month examinations. A Lan-Demets spending function with an O'Brien-Fleming type boundary will be used, with p-values for efficacy at 0.000001709 and 0.00099938 at 50% and 100% completion, respectively. Non-binding p-values for stopping due to futility at 50% and 100% completion will be 0.2336928 and 0.00099938, respectively. With the above assumptions, the trial will require 1144 participants to be enrolled. Sample size calculations were made using East version 6.

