6.11.1. Primary Efficacy Hypothesis, Endpoint, and Analysis

The primary efficacy hypothesis is that 38% Silver Diamine Fluoride (SDF) will arrest cavitated caries lesions (ICDAS 5 or 6) in primary teeth, measured by a change in dentin hardness, without a change in ICDAS severity score, after a single application (measured at 6 months). This occurs as a result of the halting of the caries disease process, which occurs very soon after application of SDF due to its strong antimicrobial and remineralizing properties.

The proportion of arrested cavities at the 6-month visit will be compared between the SDF and placebo-treated groups first using a generalized estimating equation (GEE) model with a logit link for the lesion-specific binary outcome yes/no lesion arrest at the 6-month visit, using an exchangeable correlation to account for non-independence among multiple treated lesions within a participant. The GEE model will include study site as a covariate due to stratified randomization by site.

Trial teeth that cause pain due to caries, pulpal exposure, mobility, signs of pulpal infection (abscess, fistula, swelling) will be exited from the trial and referred for appropriate care (early exit strategy), and will be considered treatment failures (non-arrest) in the analysis of the primary efficacy outcome. Treatment failures from the early exit strategy and timing of the early exit are determined from the subject disposition (withdrawal from the study with reasons related to adverse event or study tooth abscess, pulpal involvement, or pain), lesion withdrawal from the study (reason for lesion withdrawal study tooth abscess, fistula, pulpal involvement, or pain), lesion examination (notes for study tooth abscess, fistula, pulpal involvement, or pain), and adverse events. In short, any lesions removed from the trial due to the “early exit strategy” will be considered treatment failures – non-arrest of the lesion and presence of pain and/or infection – and thus will not be considered to be missing data.

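### The SAP's imputation model for lesion outcomes does not match the primary GEE: it names no child-level term, and it omits treatment, which the protocol includes

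*SAP*

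**What the plan says.** **Imputation.** Multiple imputation is the main missing-data method in both documents. Protocol 12.4.2: "The primary method for handling missing data will be to use a multiple imputation analysis". SAP 6.11 specifies fully conditional specification, 25 data sets and standard pooling. For the lesion outcomes it says "Imputations for lesion arrest and lesion pain will be based on race/ethnicity, gender, age, trial site, initial ICDAS score, tooth location", and it adds lesion arrest at earlier visits in a logistic model. Treatment is not in that list. Protocol 12.4.2 gives nearly the same list with treatment in it. SAP section 9, which lists changes from the protocol analyses, does not mention the imputation model.

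For the subject-level pain score and the family outcomes, SAP 6.11 does use a child-level arrest indicator. It names nothing of the kind for lesion arrest or lesion pain.

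**Analysis.** SAP 6.11.1 fits a logit GEE with site as covariate, "using an exchangeable correlation to account for non-independence among multiple treated lesions within a participant". SAP section 4 reports from earlier studies "an average of 4 lesions was treated per participant, with a within-participant correlation of 0.5" and plans on 3 lesions.

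**Error rate.** SAP 6.11: "The overall type I error for interim and final primary endpoint analysis is two-sided" 0.1%, and "The interim and final analyses will be conducted using p-value thresholds of 0.000001709 and 0.00099938, respectively".

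**The concern.** An imputation model should contain the features that the analysis model estimates or relies on. Here two are absent from the SAP text.

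- **Treatment.** If arm is not a predictor, missing lesions in both arms are drawn largely from a common distribution. The imputed part of the data carries little treatment difference, and the pooled odds ratio moves toward 1.
- **Child.** A missed visit usually removes all of a child's lesions together. If each is then drawn separately given the covariates, the imputed children vary less than real ones. With treatment in the model, this makes the pooled SE too small.

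The two faults act in opposite directions on the test. The primary endpoint is affected, and so are both key secondary endpoints (8-month arrest and lesion pain), which rely on the same imputation paragraph.

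**Working it through.** **Plan's own figures.** Inputs from SAP section 4: 55% versus 45%, two-sided 0.1%, 80% power, 3 lesions, correlation 0.5.

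- Lesions per arm: (3.2905·√0.5 + 0.8416·√(2·0.55·0.45))² / 0.10² = 852.
- Design effect: D = 1 + 2·0.5 = 2. Children per arm: 852·2/3 = 568, so 1136 in total, against 1144 stated.
- The two-look boundaries come out at 0.0000017086 and 0.00099936, and power at 1144 is 80.1%. The plan is reproduced.

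**Converting an SE ratio into an error rate.** Let r = pooled SE / true SD. The final threshold corresponds to z = 3.2907, so the implied two-sided error is 2(1 − Φ(3.2907·r)).

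**Closed form, missing children with no 3-month result.** Let f be the share of children missing. Variances are per arm, in units of lesion variance / (lesions × children).

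*Treatment in, lesions drawn separately:*
- Within-imputation: W = (1−f)D + f
- Between-imputation: B = f + f²/(1−f)
- Pooled: T = W + 1.04B
- True: V = D/(1−f) + B/25

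At f = 0.10: W = 1.90, B = 0.111, T = 2.016, V = 2.227, r = √(T/V) = 0.951, error 0.17%.
At f = 0.20: T = 2.060, V = 2.510, r = 0.906, error 0.29%.

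With 4 lesions (D = 2.5), the same formulas give r = 0.941 (0.19%) and 0.886 (0.36%).

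*Treatment out:* B = f and V = (1−f)D + f/25. With 3 lesions, r = √(2.004/1.804) = 1.054 at 10% and √(2.008/1.608) = 1.117 at 20%. The SE is now too large.

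**Simulation under no effect.** 8,000 trials per setting; 1144 children with 3 lesions each; correlation 0.5; whole-child missing 6-month visits; 25 imputations; child-clustered variance. The same-lesion correlation between months 3 and 6 was taken as 0.8 (an assumption). Each cell gives r, then implied error, then the simulated rejection rate at the final threshold (Monte Carlo SE about 0.035 points near 0.1%).

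| Missing at 6 months | Of these, also missing 3 months | Treatment in | Treatment out (SAP list) |
|---|---|---|---|
| 10% | none | 0.998; 0.10%; 0.13% | 1.008; 0.09%; 0.08% |
| 10% | half | 0.979; 0.13%; 0.18% | 1.025; 0.07%; 0.09% |
| 10% | all | 0.957; 0.16%; 0.18% | 1.043; 0.06%; 0.10% |
| 20% | none | 0.986; 0.12%; 0.16% | 1.038; 0.06%; 0.08% |
| 20% | half | 0.947; 0.18%; 0.21% | 1.076; 0.04%; 0.04% |
| 20% | all | 0.910; 0.28%; 0.29% | 1.119; 0.02%; 0.04% |

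**Simulation at 55% versus 45%, half of the missing children having 3-month results.**

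- Treatment out, 10% missing: log odds ratio 0.402 → 0.378 (0.378/0.402 = 0.94), power 73%.
- Treatment out, 20% missing: 0.400 → 0.352 (0.88), power 64%.
- Treatment in: no shrinkage, power 79% at both.

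The 79% is itself flattered by the SE being too small (r about 0.96 in those runs).

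**With the child as the imputation unit and treatment in**, half of the missing children having 3-month results: r = 0.994 at 10% and 1.001 at 20%, implied error 0.107% and 0.099%. The pooled SEs were 0.0998 and 0.1034. Power is therefore about Φ(0.402/0.0998 − 3.2907) = 77% and Φ(0.402/0.1034 − 3.2907) = 72%. These are the fairer comparators for 73% and 64%.

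**The case against.** **A reader might infer that the SE is too small and that the 0.1% is not held.** The documents do not support this for the SAP as written. That result needs treatment in the imputation model, and the SAP list leaves it out. With that list, r is above 1 in every setting checked and the 0.1% is held.

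There is an argument that treatment is meant to be in. The protocol lists it, section 9 records no change, and the tipping-point analysis in SAP 6.11.3 shifts the log odds for the SDF group within the same model. That makes inclusion plausible but does not establish it. The text has to settle the matter.

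**The size can also be overstated.** With treatment in, 10% missing and all 3-month results present, the effect is negligible (r = 0.998). Shared covariates and prior-visit results carry part of the within-child correlation, and observed children still enter a clustered variance. The SAP is silent on a child term; it does not say that lesions are independent. These points stand, and they limit the size.

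**The interim threshold.** By the closed form with treatment in, 0.0000017 becomes about 0.0000053 at 10% missing and 0.000015 at 20%. Those are multiples of about 3 and 9, but at most 1.5% of the 0.001 total.

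**On the other side,** missingness may exceed 10%. SAP 6.4.2 describes in-person visits that could not take place in window because of COVID-19, and SAP 6.11.3 sets out-of-window data to missing. Neither gives a share.

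**Conclusion.** The mismatch is real, and its consequence depends on a point on which the two documents disagree.

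- **SAP list (treatment out):** the test is conservative. The cost is an estimate pulled toward zero by about 6% on the log scale at 10% missing and 12% at 20%, with the power loss shown above.
- **Protocol list (treatment in), no child level:** the SE is about 0–6% too small at 10% missing (error about 0.10–0.19%). At 20% with 3 lesions it is about 1–10% too small (about 0.12–0.29%). The effect is near zero when the missing children have 3-month results and largest when they do not.

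Restoring treatment alone would exchange the first problem for the second, so both repairs belong together.

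The figures assume that whole children are missing, unrelated to outcome, and that there is no site effect. They also assume equal lesion counts and the stated 0.8 correlation between visits. The 10% is the protocol's attrition figure; 20% and the 3-month patterns are assumptions. The lesion-pain and 8-month analyses were not simulated separately.

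**What to change.** In SAP 6.11, for both lesion arrest and lesion pain:

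1. Add treatment to the imputation predictors, or impute separately by arm, in line with protocol 12.4.2.
2. In the same edit, add the child level, by a child random intercept or by entering the results of the child's other lesions as predictors.
3. If leaving treatment out was intended, record it in SAP section 9 with a reason.

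Report the site-adjusted available-case GEE, with early exits counted as failures, as a sensitivity analysis. It should not become a second condition for claiming the primary result.

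The cost is SAP wording and programming. Relative to the protocol's treatment-in list, the reported SE may become a few percent larger.
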